At week 0 visit the study patient will have a physical exam and a urine pregnancy test. The patient's AE and symptom diary should be reviewed and the clinically modified PDAI calculated. The patient's concomitant medications will be reviewed. If the study patient fulfils all inclusion criteria and does not have an exclusion criterion the study patient will be randomized to either the placebo or the FMT group and a unique study ID number will be assigned, which will appear on all medication packs.

The study patient then undergoes a pouchoscopy for evaluation of the pouch inflammation and to rule out complications in the pouch structure (e.g. strictures, isolated cuffitis, which would lead to exclusion of the trial). If all inclusion criteria are met during an endoscopically guided placebo or real FMT will be performed. Additionally, the study patient will be started on omeprazole 20 mg (1 tablet/daily) as

long as he/she undergoes oral FMT or placebo therapy. The study patient will receive 2 diaries, which need to be filled out on a daily basis, the stool diary and the adverse event diary. The stool diary should be daily completed either until Visit 8 or if the patient participates in the open label extension until visit 12OL. The adverse event diary has to be daily completed until visit 6 or visit 10OL.

At visits 2 and 4 (phone visits) the coordinator will ask the study patient if adverse events occurred and will review the adverse event diary with the study patient. The coordinator will also evaluate the clinical components of the mPDAI of the last 3 days before the phone call (stool frequency, rectal bleeding, fecal urgency/ abdominal cramping, fever) as well as the concomitant medications.

Visit 3 (site visit) the coordinator will review the adverse event diary with the study patient, and will assess the mPDAI and concomitant medication. The patient will also bring a stool sample for the stool bank, which was collected earliest on day 1 after the end of the oral or placebo FMT period.

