Calculation of mPDAI score (before pouchoscopy)

Pouchoscopy (in patients in clinical remission and no need for antibiotics only): Evaluation of endoscopic PDAI.

If patient is in clinical remission (mPDAI ≤ 4) and no need for antibiotics proceed to pouchoscopy

If patient is not in clinical remission (mPDAI > 4) or need for antibiotics or comes in due to exacerbation of symptoms with possibility to continue with open label extension. Need to restart 10 day course of antibiotics as standard of care similar to initial antibiotic treatment before the first FMT

In case of **premature withdrawal** from the study (yes, no)

If yes, reason:

- Intolerance of medication
- Lack of efficacy (need for steroids e.g. increase of steroids or re-introduction of steroids after previously successful taper)
- Severe adverse event
- Lack of patient's cooperation
- Inclusion criterion not fulfilled or exclusion criterion fulfilled coming to knowledge after recruitment
- Other reason

9. FOLLOW-UP VISITS OF PATIENTS IN REMISSION AT WEEK 4 OR NOT PARTICPATING IN THE OPEN LABEL EXTENSION

• Visit 6: Phone visit week 6 (42 +/- 3 days after first transplant)

Formal aspects:

Adverse events (review adverse events diary, last day of filling out the diary is 28 days after end of oral FMT, which is around week 6; patient needs to be advised to bring filled out diaries to visit 7)

Concomitant medication

Calculation of clinical mPDAI (stool frequency, rectal bleeding, fecal urgency/abdominal cramping, fever)

• Visit 7: Site visit week 8 (56 +/- 5 days after first transplant)

Examinations

Vital signs: blood pressure (mm Hg), heart rate (min-1), weight (kg), temperature

Physical examination:

- Head (including ENT and eyes)
- Lymphatic system
- Endocrine system
- Lungs and respiratory tract
- Peripheral vascular system
- Cardiovascular system

- Gastrointestinal tract, liver, spleen
- Urogenital system
- Nervous system
- Muscular and skeletal system
- Skin and connective tissue
- Other

each: actual status: Present finding / normal condition / not examined

Measurement of laboratory parameters

Hematology Serum chemistry

Stool collection: Bring to clinic.

Formal aspects:

Concomitant medication

Adverse events (adverse events diary filled out until visit 6)

Calculation of mPDAI score

Reminder stool collection and bring in stool week 16.

Collect adverse event diary (filled out until week 6)

• Visit 8: Site visit week 16 (112 +/- 7 days after first transplant)

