Pouchoscopy will be performed to evaluate the pouch, prepouch ileal segment and the cuff. The pouch and prepouch inflammation will be graded according mPDAI (see attachment).

• Laboratory parameters

All laboratory analyses will be carried out in at the local laboratory of the investigational site.

Acute phase reactants (nonspecific inflammatory markers)

C-reactive protein (CRP)

Hematology:

Blood count (erythrocytes, hemoglobin, hematocrit, leukocytes, platelets)

Serum chemistry:

Kidney function: creatinine

Liver function (alanine aminotransferase {ALT}, aspartate aminotransferase {AST}, alkaline phosphatase, bilirubin)

Urine pregnancy test screening visit and in the 24 hours before FMT

12. RECORDING OF COMPLIANCE

Compliance will be assessed by checking the study medication (containers) returned at the follow-up visits and the final visit by the investigator.

All returned containers will be counted by the study coordinator and the number will be documented in the CRF.

13. ADVERSE EVENTS

• Definitions

Adverse events (AEs)

Adverse events (AEs) will be recorded at each regular scheduled study visit or study phone contact in the study patient record (source document) as well as on a specific AE form on the CRF.

An AE is any untoward medical occurrence in a study patient or clinical investigation subject administered a pharmaceutical product and which does not necessarily have a causal relationship with this treatment. An AE can therefore be any unfavourable and unintended sign (including an abnormal laboratory finding), symptom, or disease temporally associated with the use of a medicinal product, whether or not related to the medicinal product, e.g.:

- any new diagnosis
- any symptom that requires medical clarification or leads to in-patient admission (surgery or accident)
- any suspected adverse drug reaction (ADR)
- any symptom that appears on the study patient's medical records
- any event related in time with the application of the study medication and affecting the health of the study patient (including laboratory value changes)

Serious Adverse Events (SAE)

A serious adverse event (experience) is any untoward medical occurrence that at any dose:

- results in death
- is life-threatening
- requires inpatient hospitalization or prolongation of existing hospitalization
- results in persistent or significant disability/incapacity

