14. DOCUMENTATION AND REPORTING OF ADVERSE EVENTS

The study patients will be instructed to contact the investigator, if any serious or unexpected AE occurs, so that appropriate action can be taken.

Moreover, the investigator must ask at each follow-up visit a generally worded question without searching for any special symptoms, e.g. "Has your state of health worsened since we last met?" If the answer to this question is "no", no further questions will be asked. If the answer to the question is "yes", the investigator will document the nature, time, severity, seriousness and duration as well as the causality of the AE. For each AE a specific AE documentation form will be provided, which should be completed by the PI as an initial report. The report must contain a detailed description of the symptoms observed and the concomitant treatment administered. Furthermore, the investigator must comment on a possible causative relationship between the AE and the trial medication. Each AE must be followed until it is resolved or can be explained satisfactory.

The following has to be documented for each AE:

- Nature of the event
- Time of onset: date, time
- Concomitant treatment: product (generic name), indication, dosage, dosage interval, presentation, mode of administration, administration regimen
- Duration of the AE
- Severity
- Seriousness
- Causality
- Outcome

Severity

The severity is evaluated as follows:

- 1. Mild: event/symptom does not interfere with normal daily activities
- 2. Moderate: event/symptom interferes with normal daily activities

3. Severe: - event/symptom prevents normal daily activities

Causality

The relationship between an AE and the study medication is classified according to the WHO classification:

Certain

A clinical event, including laboratory test abnormality, is occurring in a plausible time relationship to drug administration, and which concurrent disease or other drugs or chemicals cannot explain. The response of the study patient to withdrawal of the drug should be clinically plausible. The event must be definite pharmacologically or phenomenologically, using a satisfactory rechallenge procedure if necessary.

Probable/Likely

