The primary endpoint is the evaluation of safety and tolerability of FMT in patients with ADP. Secondary endpoints are endoscopic and clinical remission at week 4 in conjunction with no need for antibiotic therapy, clinical response and remission and no need for antibiotics at week 4,8 and 16, endoscopic improvement of pouchitis and quantitative changes of calprotectin after the initial FMT. All subjects with missing data for determination of endpoint status will be considered as a non-responder in the intention-to-treat analysis. For dichotomous outcomes we will compute the percentage of subjects having the event along with a 95% confidence interval. For continuous outcomes we will compute the mean and a 95% confidence interval for the mean as well as descriptive statistics such as median, range and upper and lower quartiles. In addition to computing these measures for all 20 subjects, we will compute them for subgroups of interest (e.g. endoscopic active vs inactive ADP). These estimates can then be used in the planning of a larger, hypothesis-based study.

• Sample size calculation

This trial is designed as a proof-of-concept study of FMT therapy, not a definitive evaluation of FMT therapy in patients with ADP. The goal is to evaluate the safety and feasibility of such a trial, as well as to estimate the effect sizes in placebo and FMT therapy groups in order to accurately estimate the sample size needed for subsequent evaluation in a larger definitive trial. Nonetheless, we estimated the minimum effect size this pilot study can detect. We assume a placebo remission rate (defined as clinical remission and no need for antibiotics) of 10%. The low placebo response rate is based on the inclusion criterion, which selects only patients needing continuous or recurrent antibiotic therapy in the setting of ADP. With a follow-up of 16 weeks with the requirement of clinical remission without antibiotic therapy at end of follow-up, a placebo response rate beyond 10% is highly unlikely. The recent case series of Stallmach et al. suggests an antibiotic-free remission rate of 80% and a response rate of 100% in the setting of repeated FMT.⁴⁹ With 20 patients (1:1 randomization), and a placebo response rate of 10%, we will have 80% power to detect an effect difference of 67.5%, that is, an antibiotic-free remission rate

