25. ADVERSE EVENT DIARY

Front pages of diary

Safety and efficacy of fecal microbiome transplantation (FMT) in the treatment of antibiotic dependent pouchitis (ADP)

Record of Side Effects

This diary is one way researchers will get information from you regarding any possible problems or side effects in this study.

- What you are going to do is simple. Just keep a record of any unpleasant thing that happens to you while you are in the study, before, during, and after we have completed the stool transplant. We even want you to record things that do not seem to be part of the stool therapy, at all.
- When do you start? When do you end? You will complete one entry per day during the time of oral treatment with the FMT capsule (14 days) as well as daily for 28 days after the oral treatment stopped.
- What do you look for? What do you report? Any symptom or problem whether or not it may be from the medicine, stool therapy. This could include: fever, abdominal pain, a big belly, lots of gas, diarrhea, nosebleeds, and anything else you know is not quite right.
- What will you do? In the first 42 days after the initial endoscopic transplant, you will report some of the specific things that have bothered you by checking the boxes in the diary (see below). You can also write any other problems that you may have had during that time. Additionally, you will record your temperature once for each day for the 42 days after the initial endoscopic transplant, unless you feel hot. If you feel hot, please take your temperature again. Please make sure to record the highest temperature taken that day if you take it more than once.

How will you record it? Like this...

EVENT	DATE OF ONSET	INTENSITY	ACTION TAKEN	MEDICATION	DATE RESOLVED
Fever	3/1/12	3	Missed 2 days of school	Tylenol-200mg	3/3/12
Sore throat	3/5/12	1	None	None	3/6/12

OTHER SYMPTOMS

Record each symptom at its *worst* level for each day.

For example, a sore throat that starts at 'Grade 1" but increases to 'Grade 2' should be recorded as 'Grade 2".

Examples of Grades:

Grade 1 – Mild: I noticed the symptom. It did not keep me from doing my normal activities.

Grade 2 – Moderate: I noticed the symptom and it kept me from doing some of my normal activities.

Grade 3 – Severe: I really noticed the symptom and it kept me from doing activities that I wanted or needed to do.

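### The stop rule in section 14 is narrower than the protocol's own AE definition and is not reconciled with the diary review, so mild or resolved AEs can go unrecorded, mainly after about day 42

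*Combined protocol and SAP*

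**What the plan says.** Section 14 (Documentation and reporting of adverse events) requires the investigator, at each follow-up visit, to put "a generally worded question without searching for any special symptoms". The example given is "Has your state of health worsened since we last met". If the patient says no, "no further questions will be asked". If the patient says yes, the nature, timing, severity, seriousness, duration and causality are documented.

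Other sections collect AEs without that condition:

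- Section 13 says AEs "will be recorded at each regular scheduled study visit or study phone contact".
- In section 7 the coordinator asks whether AEs occurred and "will review the adverse event diary with the study patient".
- The diary instructions in section 25 tell the patient: "We even want you to record things that do not seem to be part of the stool therapy, at all".
- The AE diary runs for the 14 days of oral treatment plus 28 days. Visit 7 in section 9 reflects its end: "Adverse events (adverse events diary filled out until visit 6".

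On the weight of these data, section 20 states: "The primary endpoint is the evaluation of safety and tolerability of FMT in patients with ADP". AEs by body system are listed there with discontinuations and laboratory changes.

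**The concern.** The section 14 question asks about overall worsening, whereas the protocol defines an AE as any unfavourable sign, symptom or disease, related or not. A patient can have had an AE and still truthfully say that overall health is no worse. Under the stop rule, that answer ends the inquiry. The visit sections point the other way, and nothing says which procedure governs or how a diary entry reaches the AE form when the answer is no. Two staff members, each following a different section, could record different AE counts for the same patient. At stake is the completeness of one component of the primary endpoint, and of the AE listings that go to the safety officer and the DSMB under section 17.

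**Working it through.** The documents give no figure for AE frequency or AE capture, so there is no stated value to reproduce on this point. The only design figure is 80% power for remission of 77.5% against 10% with 10 per arm. Exact enumeration with the two-sided Fisher test gives 0.802, and nothing below changes it.

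**Step 1: the gate against the definition.** Section 13 counts any untoward occurrence. Section 14 grades as mild an event that leaves daily activities unaffected. Section 13 lists the reactions expected in IBD patients as mild flu symptoms, abdominal pain and diarrhea, all transitory. An event that was mild, or that resolved before the visit, meets the definition but need not make a patient report worse health. The question is therefore least sensitive to the kind of event the protocol expects.

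**Step 2: section 14 against the visit sections.** Where the patient answers yes, the two routes agree. Where the patient answers no but the diary holds an entry, section 14 says to stop while sections 7 to 10 have the diary reviewed. No sentence settles that case. The scales do not settle it either: the diary has four intensity grades, section 14 has three severity levels, and no mapping is given.

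**Step 3: how much follow-up lacks the AE diary.**

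- Diary length: 14 + 28 = 42 days (sections 21 and 25).
- Last full AE review: visit 8, day 112. Week 24 covers serious AEs only.
- Without AE diary: 112 − 42 = 70 days; 70 / 112 = 62.5%.
- Gap between visits 7 and 8: 112 − 56 = 56 days.
- The open-label visits have the same spacing, counted from the second transplant.

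**Step 4: what remains after day 42.**

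| Visit | AE item | Stool diary | mPDAI, concomitant medication | Physical exam, blood tests |
|---|---|---|---|---|
| 7 / 11OL | yes | yes | yes | yes |
| 8 / 12OL | yes | yes | yes | no |

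The stool diary (section 24) records stool number, blood, cramps or urgency, and fever. It does not ask about nausea or vomiting, flu-like symptoms without fever, or events outside the gut. It serves the mPDAI, and no text says its entries are assessed as AEs. These are partial backstops.

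**Step 5: sensitivity of the estimate.** With 20 patients randomized 1:1 there are 10 per arm. One patient whose only AE is missed lowers that arm's percentage with an AE by 1/10 = 10 points, and the percentage over all 20 by 1/20 = 5 points. How many such patients there would be cannot be derived. If the diary and visit items catch everything, the number is zero.

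**The case against.** The strongest reply is that the two routes complement each other. Section 14 binds the investigator and adds its question to patient self-report; the wording is only an example, and reviewing a diary is not asking a further question. On that reading nothing is lost through day 42, which covers treatment and the 28 days after it. This stands in part: the fault is an unreconciled rule, not an outright contradiction. It does not dispose of the stop itself, because the example softens the wording of the question but not the instruction to end there.

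Other points also stand. Section 7 lists review of AEs at visits 7 and 8 without a gate. Patients are told to report serious or unexpected AEs themselves. Discontinuations and laboratory changes do not depend on the question. Asking without leading is a deliberate choice and worth keeping.

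A reader might go further and infer that the rule makes FMT look safer: FMT patients in remission answer no, and relapsing placebo patients answer yes and are asked about everything. The documents do not support this as a finding, for four reasons:

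- Through day 42 the AE diary is reviewed in both arms.
- Patients not in remission at week 4, or who flare before then, are offered open-label FMT and, if they accept, start a new AE diary. Visits 7 and 8 then hold patients in remission and those who declined, and visits 11OL and 12OL have no placebo group.
- All patients have at least 10 days of antibiotics before FMT, so a patient in remission may be stable rather than improving, and a new symptom could well prompt a yes.
- Any figure built on the remission rates would need an AE rate and a rate of missed AEs that the documents do not give. The 77.5% is the rate the trial could detect, not a forecast.

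Patients who decline the extension, and relapses after week 4, leave some residual risk.

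**Conclusion.** The point holds as a correctable weakness in AE ascertainment. Taken literally, the stop rule can under-record mild or resolved AEs, mainly at visits 7, 8, 11OL and 12OL, where no AE diary covers the preceding weeks. Before then, loss occurs only if section 14 is read as overriding the diary. The exposed window is 62.5% of the time to the last full AE review, but that is a share of time, not of events; if AEs cluster early, the share of events exposed is smaller. A difference between arms in favour of FMT is a possible risk of unknown size, and no point estimate for it should be quoted. Sample size and power are unaffected. Section 20 plans percentages with confidence intervals and names no between-arm test for AEs, so the practical consequence is a possibly low AE percentage rather than a wrong test result.

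**What to change.** 1. In section 14, delete the instruction to stop on a negative answer.
2. Keep a non-leading question but make it open: any new or worse symptom, illness or medicine since the last contact. Use it at every visit, including 7, 8, 11OL and 12OL.
3. State that diary review takes place whatever the answer, and that every AE-diary entry is assessed for the CRF AE form.

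The cost is two sentences and a CRF prompt, with slightly more minor AEs to record. No change to sample size, visits or analysis is needed.

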16. WITHDRAWAL CRITERIA

• Criteria in individual cases

Any study patient can withdraw from the study at any time without personal disadvantages and without having to give a reason. The time of withdrawal, the results available up to that time, and, if known, the reason for withdrawal must be documented on the CRF.

The investigator can also discontinue the study after considering the risk-to-benefit ratio, if he/she no longer considers the further participation of the study patient justifiable. The date of and the primary reason for the withdrawal as well as the observations available at the time of withdrawal are to be documented on the CRF.

Reasons leading to the withdrawal of a study patient can include the following (primary reason must be determined):

- Development of a SAE that is thought to be likely secondary to study drug or study intervention.
- Development of an AE with ≥ grade 3 toxicity, using the FDA toxicity grading scale for preventive vaccines (

If the PI or DSMB believes it is no longer in the subject's best interest to continue participation in the study. Examples include:

- A serious or unexpected adverse event
- Serious inter-current illness, or
- Progression of disease that requires alternative treatment.
- The subject no longer meets the inclusion criteria.
- Lack of compliance with study procedures or study treatment, as determined by the PI.

In all study patients who finish the study prematurely, a withdrawal examination should be carried out within 3 weeks after the last application of the study medication. The withdrawal examination must be conducted as a final examination and documented in the CRF. It is most important to calculate at least the final mPDAI score for each study patient. If possible, an endoscopy with biopsies according to the protocol should be performed and blood samples for hematology and serum chemistry should be taken.

The investigator will continue to observe study patients withdrawn from the study because of intolerable AEs until the findings have been clarified.

• Criteria for the termination of the whole study

If serious safety concerns arise, the coordinating investigator can terminate or interrupt the study by agreement with the sponsor and the DSMB. If new information on the risk-to-benefit ratio of the drug or on the treatment methods used in the study is obtained in the meantime, the coordinating investigator reserves the right to interrupt or terminate the project by agreement with the sponsor. Premature termination is also possible if the coordinating investigator, or the investigators and the sponsor if study patient recruitment is insufficient and cannot be expedited by appropriate measures.

The study should also be stopped or paused until thorough review of all safety data by the DSMB for the following:

• An SAE occurs in at least one subject in which the SAE is determined to be possibly, probably, or definitely related to test treatment.

• The same grade 3 or higher AE assessed as possibly, probably, or definitively related, occurring in two or more subjects, using the FDA toxicity grading scale for preventive vaccines.

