A clinical event, including laboratory test abnormality, with a reasonable time sequence to the administration of the drug, unlikely to be attributed to concurrent disease or other drugs or chemicals, and which follows a clinically reasonable response on withdrawal (de challenge). Rechallenge information is not required to fulfil this definition.

Possible

A clinical event, including laboratory test abnormality, with a reasonable time sequence to administration of the drug, but which could also be explained by concurrent disease or other drugs or chemicals. Information on drug withdrawal may be lacking or unclear.

Unlikely

A clinical event, including laboratory test abnormality, with a temporal relationship to drug administration which makes a causal relationship improbable, and in which other drugs, chemicals or underlying disease provide plausible explanations.

Conditional/Unclassified

A clinical event, including laboratory test abnormality, reported as an adverse reaction, about which more data are essential for a proper assessment or the additional data are under examination.

Not assessable / Unclassifiable

A report suggesting an adverse reaction, which cannot be judged because information is insufficient or contradictory, and which cannot be supplemented or verified.

As an alternative to the above-mentioned WHO assessments, the following assessment can be made:

Not related

There is sufficient information available to show that the etiology is unrelated to the study medication.

Measures at the onset of adverse events

Measures at the onset of adverse events are classified and described as follows:

- 1) None, i.e. the study medication was not changed
- 2) The dose of the study medication was reduced
- 3) The study medication was withdrawn and/or
- 4) Other measures (clear text)

The course and outcome of the adverse event will be commented on as follows:

- Recovered without sequelae
- Not yet recovered
- Recovered with sequelae
- Fatal
 - Documentation and Reporting of Serious Adverse Events

On enrolment in the study, the study patients will be instructed to contact the investigator if a serious or unexpected AE occurs, so that appropriate measures can be taken.

Any SAE (including death, irrespective of the cause) occurring during or for up to 14 days after the end of the study will be immediately reviewed by the PI, i.e. within 24 hours.

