A specific SAE documentation form will be provided. In case of an SAE, this form will be completed and reviewed by the PI as an initial report, and if the SAE is judged to be possible related or related to study drug will be sent (via fax) to the IRB of the University of North Carolina. The report must contain a detailed description of the symptoms observed and the concomitant treatment administered. Furthermore, the investigator must comment on a possible causative relationship between the AE and the trial medication. Each SAE must be followed until it is resolved or can be explained satisfactorily.

The general procedure for the observation, collection and analysis of drug risks (regulatory affairs) in conformity with the appropriate national Drug Law shall apply without qualification.

In accordance with drug safety and national requirements, the study PI will inform the IRB of the study at the University of North Carolina and will make sure that the involved persons will obtain adequate information.

The following instructions must be heeded:

In the case of an intolerable SAE, the study patient must, at the decision of the investigator, be withdrawn from the clinical trial, and symptomatic treatment must be administered. The measures taken must be recorded on the CRF.

In accordance with local legislation, the investigators will submit copies of the final SAE-report to the Regulatory Authorities concerned, if necessary.

15. ABNORMAL LABORATORY RESULTS

All laboratory values outside of the normal range will be repeated as judged appropriate to ensure the validity of the abnormal result. The investigator will document all laboratory values on the relevant page of the CRF and will assess the etiology of the clinically relevant abnormal laboratory values.

Clinically relevant abnormal laboratory values are only documented on the AE form of the CRF, if the study patient is discontinued, hospitalized, or, in the investigator's opinion, it should be considered as an AE.

Abnormal laboratory results caused by ulcerative colitis should not be reported on the AE form.

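### Section 16 lets a serious or severe adverse event end a patient's time in the study with a final examination, and this conflicts with the sections that keep such patients on scheduled safety visits

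*Combined protocol and SAP*

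**What the plan says.** Section 16, under the criteria for individual cases, introduces its list with "Reasons leading to the withdrawal of a study patient can include the following". The list contains "Development of a SAE that is thought to be likely secondary to study drug or study intervention" and, as a separate entry, an AE of grade 3 or higher with no requirement that it be related to treatment. The surrounding text is about ending participation in the study. Section 14 says of an intolerable SAE that "the study patient must, at the decision of the investigator, be withdrawn from the clinical trial". The visit 5 form in section 8 likewise records drug intolerance and a severe adverse event as reasons for leaving the study early.

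For everyone who finishes early, section 16 asks that "a withdrawal examination should be carried out within 3 weeks after the last application of the study medication", and then adds: "The withdrawal examination must be conducted as a final examination and documented in the CRF". It schedules no visit after that. The one continuation it gives is: "The investigator will continue to observe study patients withdrawn from the study because of intolerable AEs until the findings have been clarified".

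Other text points the other way. In section 7, the heading of the early-termination part names adverse events beside flare and unwillingness to continue. That part ends by sending patients who decline the open-label part to visits 6-9. The title of section 9 covers all patients who do not take part in the extension, with no exception for AE cases. For the open-label phase, section 7 keeps patients on the same schedule after a recurrence of disease and says nothing about AE withdrawals.

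**The concern.** Safety and tolerability is the primary endpoint (sections 5 and 20). The trial has 20 patients randomized 1:1, so each patient is 10% of an arm. The patients touched by the withdrawal text are those who have already had an important event. They are also the ones in whom a further or delayed event would be most informative.

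An investigator who follows section 16 could treat the examination as the last contact. One who follows sections 7 and 9 would keep a blinded-phase patient on visits 6-9. No sentence says which applies to a patient withdrawn for an SAE or a grade 3 AE, and for the open-label phase there is not even a competing instruction. What is at stake is the scheduled prompting for new or late events: the AE questions at visits and calls, the blood tests at week 8 or visit 11OL, and the closing SAE call. Section 20 counts missing efficacy status as non-response, but nothing comparable stands in for safety observation that was never made.

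**Working it through.** The plan gives no figure for this point, so the check compares texts and then counts days on the visit schedule.

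**Texts side by side**

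- *What is the patient withdrawn from?* Sections 14 and 16 and the visit 5 form: the trial or study. Section 14 does list stopping the medication as a separate action at the onset of an AE ("The study medication was withdrawn and/or", where the last words lead into the next entry). The protocol therefore knows the distinction, but section 16 attaches no follow-up rule to it.
- *What follows, blinded phase?* Section 16: a final examination. Sections 7 and 9: visits 6-9 for those not in the extension. The body text under the section 7 heading describes only recurrence of pouchitis, and the same heading covers patients unwilling to continue in the study, who cannot all be meant for visits 6-9.
- *What follows, open-label phase?* Section 16: a final examination. Section 7: the schedule is kept for worsening disease only.
- *Is early exit after dosing foreseen?* Yes. The section 21 charts for the observation phase and the extension have an early-termination column, and footnote g extends it to visits 6-8 and 6OL-12OL.

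**Inputs for the day count**

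- Oral course 14 days (section 1), so the last dose is taken as day 14.
- Examination within 21 days of the last dose (section 16), placed on the last permitted day.
- Blinded-phase contacts after day 0: visits 2-9 on days 7, 15, 26, 28, 42, 56, 112 and 168, which is 8 contacts (section 21).
- Open-label contacts after the second transplant on day 38: visits 7OL-13OL on days 46, 53, 66, 80, 94, 150 and 206, which is 7 contacts (section 21).
- Full AE review runs to day 112 after a transplant. The last call, at day 168, reviews SAEs only.
- The AE diary runs for 14 + 28 = 42 days, which matches the 42 days stated in section 25.

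**Blinded phase**

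- Latest examination: 14 + 21 = day 35.
- Contacts after day 35: days 42, 56, 112 and 168, so 4 of 8.
- AE review at risk: 112 - 35 = 77 days; 77/112 = 69%.
- SAE review at risk: 168 - 35 = 133 days; 133/168 = 79%.
- AE diary at risk: 42 - 35 = 7 days.

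**Open-label phase**

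- Latest examination: 38 + 14 + 21 = day 73.
- Contacts after day 73: days 80, 94, 150 and 206, so 4 of 7.
- AE review at risk: 150 - 73 = 77 of 112 days. SAE review at risk: 206 - 73 = 133 of 168 days.

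**Sensitivity**

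- If the last dose is counted as day 13, the examination falls by day 34 and the losses are 78 and 134 days.
- If only the endoscopic FMT was given (last dose day 0), the examination is due by day 21. Then 168 - 21 = 147 of 168 days (87.5%) are at risk and visit 5 on day 28 is exposed too. The open-label equivalent is 38 + 21 = day 59, which also exposes visit 9OL on day 66.
- Withdrawal later than the dates above loses less.

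**The case against.** For the blinded phase, the documents come close to answering the question. The section 7 heading names adverse events, its closing sentence leads to visits 6-9, and the section 9 title makes no exception. The words about a final examination can be read as describing its content, since the sentences that follow list the final mPDAI, endoscopy and bloods. Nothing in section 16 cancels a later visit. Withdrawal is optional under section 16 and left to the investigator under section 14.

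There are also safety nets. Known AEs and SAEs are followed until resolved or explained, and on enrolment "the study patients will be instructed to contact the investigator if a serious or unexpected AE occurs". One related SAE pauses or stops the study for DSMB review, and a safety officer sees cumulative AE reports monthly.

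Most of this stands. A reader might infer that the plan deliberately drops patients with serious events from safety follow-up; the documents do not support that, because sections 7 and 9 point the other way and withdrawal is discretionary. A reader might also take the lost days as days without safety capture. They are days without scheduled prompting, while self-reporting and observation of known events go on. Finally, a reader might count lost access to open-label FMT as a harm. Withholding a second FMT after a likely related SAE is sensible, and section 6 itself excludes patients with an adverse event attributable to a previous FMT.

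What the objection does not remove is the conflict between sections, the silence for AE withdrawals in the open-label phase, and the lack of scheduled detection of new events once section 16 is applied. Section 14 also provides for SAE review up to 14 days after the end of the study, but that end is not defined for a withdrawn patient.

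**Conclusion.** The point holds as a conflict between sections that can shorten scheduled safety follow-up, and it rates as a cheap improvement. For each patient withdrawn by the final examination after a completed course, up to four contacts are at risk (visits 6-9, or 10OL-13OL), with up to 77 of 112 AE-review days and 133 of 168 SAE-review days.

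These figures assume that section 16 is taken to override sections 7 and 9, that the last dose is on about day 14 of the course, and that the examination falls on the last permitted day. The documents do not fix how many of the 20 patients would be affected, and it may be none. The open-label phase is the weaker of the two, because there no other text clearly keeps AE withdrawals on schedule.

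**What to change.** In section 16, and in the matching sentence of section 14, state the following:

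- These reasons stop study treatment only, including any open-label FMT.
- The remaining scheduled visits (to visit 9, or to 13OL) are kept for AE and SAE review, blood tests and the diary-based clinical mPDAI, unless the patient withdraws consent, or the PI or DSMB judges continued contact not in the patient's interest.
- Pouchoscopy is done only if medically appropriate, so that a patient with an SAE from the study intervention is not bound to the one at visit 9OL.
- The examination within 3 weeks of the last dose is an end-of-treatment examination.

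This brings section 16 into line with sections 7 and 9 and gives the open-label phase an express rule. The cost is a short amendment and up to four already scheduled contacts (two by phone, two on site) per affected patient who completed the course, slightly more if dosing stopped early. No new procedures are needed.
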